8.2 SAMPLE SIZE DETERMINATION

No preliminary data is available on ESRD patients with this device. Heinemann et al.⁴² studied subjects with hypoglycemia treated with insulin. The authors reported medians and interquartile ranges of this outcome under RT-CGM or usual care. Based on these preliminary data, we approximated the standard deviation (SD) of our primary outcome under the normality assumption. This suggests 6.45% as a conservative upper bound for the SD. Assuming 10% attrition rate and 6.45% as the SD of the primary outcome, recruiting 45 subjects would give 90% power to detect a mean difference in percentage time in hypoglycemia range which equals 4.8%, based on a two-sided t-test for a two by two cross-over design, with alpha=0.05.

8.3 POPULATIONS FOR ANALYSES

- Intention-to-Treat (ITT) Analysis Dataset (i.e., all randomized participants)
- Modified Intention-to-Treat Analysis Dataset (e.g., participants who use the CGM for at least 10 days of study intervention and/or have acceptable amount of follow-up outcome data)
- Safety Analysis Dataset: defines the subset of participants for whom safety analyses will be conducted (e.g., participants who use the CGM for at least 10 days of study intervention)
- Per-Protocol Analysis Dataset: defines a subset of the participants in the full analysis (ITT) set who complied with the protocol sufficiently to ensure that these data would be likely to represent the effects of study intervention according to the underlying scientific model (e.g., participants who took at least 80% of study intervention for 80% of the days within the maintenance period)

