1.d. Sensor Insertion: We will use a commercially available (FDA approved) glucose sensor. We will use an aseptic technique following manufacturer recommendations. After insertion of the sensors, providers will ensure proper hemostasis is achieved. Sensors will be removed if prolonged bleeding or severe pain occurs. It's uncommon but inserting the sensor could cause infection (<1%), bleeding or pain (~10%), and wearing the adhesive patch can irritate the skin (~10% on prior studies). We will avoid insertion over irritated or damaged skin, exclude subjects who are sensitive to adhesive and use an aseptic technique to avoid this. The principal investigator and our study team is experienced in performing studies using CGM in high-risk population (hospitalized, acutely ill patients), with minimal risk involved.

1.e. Alternative Treatments and procedures. Patients with diabetes do not need to be part of this study. Monitoring POC BG is standard of care and all subjects in this study will be instructed to perform it. CGM is also indicated for monitoring glycemia and to assist with treatment adjustments in subjects with diabetes. This will be made clear before any subject signs the

informed consent. If subjects do not want to participate in the study, they will receive care that they are otherwise entitled to without bias.

1.f. Sensors Contraindication: Sensors will be removed before MRI, CT, diathermy procedures, per manufacture instructions.

1.g. Sensor precautions: Avoid using sunscreen or insect repellents from having contact with sensor.

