4 STUDY DESIGN

4.1 OVERALL DESIGN

Aim 1a. To examine overall glycemic control, as measured by CGM and POC (standard of care, as available), among ESRD patients with DM2 treated with insulin. In this longitudinal cohort study, we will examine the overall glycemic control among insulin-treated patients receiving hemodialysis.

Hypothesis: Patients with DM2 on hemodialysis will have wide glycemic excursions, characterized by increased rates of symptomatic and asymptomatic hypoglycemia, with subsequent rebound hyperglycemic excursions and overall high glycemic variability.

Aim 1b. To assess the accuracy of the CGM system, as determined by differences in mean absolute relative difference (MARD), compared to time-matched paired glucoses measured by POC BG (standard of care) and YSI 2900 analyzer glucose sample in patients with DM2 on hemodialysis. In this comparative study, we will analyze glucoses obtained by CGM to the reference glucoses obtained by home POC BG and YSI obtained during dialysis sessions among subjects participating in Aim 1a.

Hypothesis: We hypothesize that the overall accuracy in patients with DM on dialysis will be within <12% MARD, compared to the standard of care POC BG and YSI .

Study Overview/Procedures for Aim 1a and Aim 1b:

In this prospective observational cohort study, we will determine daily glucose concentration, rates of hypoglycemia (overall, nocturnal and asymptomatic), hyperglycemia and GV measures detected by real-time CGM in patients treated by maintenance dialysis compared to POC BG (standard-of-care, as available). Up to 100 subjects could be recruited, until a total of 40 insulin-treated patients with DM2 on hemodialysis have completed all procedures for this Aim. After obtaining informed consent (Aim 1a), we will collect baseline demographics, and available laboratory data from the electronic medical record and place a blinded CGM (Day 1) for 10 days. Subjects will complete a food record for three (3) days for caloric intake analysis, one (1) on a pre-dialysis day, one (1) on dialysis day and one (1) the day after a dialysis day⁶⁵. No therapy adjustment or interventions will be made by the study team during this period. Glycemic monitoring and treatment of dysglycemia will be performed by the primary care team following standard-of-care.

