5.6 STUDY INTERVENTION(S) ADMINISTRATION

5.6.1 STUDY INTERVENTION DESCRIPTION

Aim 1. Study Overview/Procedures for Aim 1a and Aim 1b: In this prospective observational cohort study, we will determine daily glucose concentration, rates of hypoglycemia (overall, nocturnal and asymptomatic), hyperglycemia and GV measures detected by real-time CGM in patients treated by maintenance dialysis compared to POC BG (standard-of-care, as available). Up to 100 subjects maybe consented/recruited, until a total of 40 insulin-treated patients with DM2 on hemodialysis have completed all procedures for this aim. After obtaining informed consent (Aim 1a), we will collect baseline demographics, and available laboratory data and place a blinded CGM (Day 1) for 10 days. Subjects will complete a food record for three (3) days for caloric intake analysis, one (1) on a pre-dialysis day, one (1) on dialysis day and one (1) after a dialysis day⁶⁵. No therapy adjustment or interventions will be made by the study team during this period. Glycemic monitoring and treatment of dysglycemia will be performed by the primary care team following standard-of-care. These results will provide detailed understanding of glycemic excursions among patients treated with insulin on hemodialysis. The information collected in these studies will be used as preliminary data for future intervention studies to control hyperglycemia, hypoglycemia and GV.

Study Design:

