Aim 2. Study Overview/Procedures (Randomized Controlled Study, RCT): In this pilot, cross-over, randomized, controlled trial (Fig. 2), patients with type 2 DM treated with insulin, on hemodialysis will use a real-time/personal CGM for 4 weeks (Intervention-Control Group), then 2 weeks of wash-out period, and cross over to use a blinded CGM for 4 weeks; and vice versa (Control-Intervention Group). Participants will be trained to replace the G6 sensors at home during those 4 weeks, as usually performed in clinical practice. Dexcom G6 monitors glucose continuously (24 hrs) and displays real-time glucose values, glucose trends/arrows and alarms, including the “urgent low soon” alarm (predictive of hypoglycemia < 55 mg/dL within the preceding 20 minutes). We hypothesize that the use of CGM will prevent hypoglycemia, and potentially rebound hyperglycemia, and consequently decreased glycemic variability during and between dialysis sessions in insulin-treated patients with type 2 DM. These results may provide novel data on glucose monitoring in this population that will serve as basis for future intervention studies to control hyperglycemia, while preventing hypoglycemia.

Study Design: In this cross-over RCT (Fig. 2), each subject will receive the intervention (24-hours real-time CGM) and conventional/standard-of-care therapy (POC BG), at different study

times. The cross-over design will reduce costs and simplify recruitment activities, while increasing power, since each subject will be studied with both treatment strategies, and serve as controls. [name] have experience in RCT design, implementation and has previously published land-mark studies with a cross-over design⁷⁰. There will be a wash-out period to avoid the potential carry-over effects of the CGM intervention, Phase I. Hypoglycemic excursions in hemodialysis patients treated with insulin are common, and thus 4 weeks of intervention with 2 weeks of wash-out period is expected to improve retention

Description of Study Visits for Aim 2a.

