6 STUDY INTERVENTION DISCONTINUATION AND PARTICIPANT DISCONTINUATION/WITHDRAWAL

6.1 DISCONTINUATION OF STUDY INTERVENTION

Participation in the clinical study will be terminated for each participant following the last visit or when all AEs have been resolved or considered ongoing but stable. Prior to this time, participants may voluntarily withdraw at any point in the study or the Investigator and/or Sponsor may determine that it is in the best interest of the participant to be terminated from the study.

Reasons for withdrawal of participant from the study include, but are not limited, to the following:

- a) In the opinion of the Investigator, the participant's health or safety would be compromised by continuing in the study
- b) In the opinion of the Investigator, it is in the participant's best interest to discontinue participation in the study
- c) During the study, (female) participant becomes pregnant

However, discontinuation of the study intervention (CGM) does not equate with discontinuation from the study and every effort will be made to retain participants in the study for the primary outcome assessment, even if CGM is discontinued.

The clinical study in its entirety will be considered complete upon receipt of reports from study monitoring activities, completion of site closeout visits, and issuance of a clinical study report. The clinical study report will include all safety and efficacy data.

Insertion of the CGM sensor will be performed per manufacture instructions and following an aseptic technique. After insertion of the sensors, providers will ensure proper hemostasis is achieved. Sensors will be removed if prolonged bleeding or severe pain occurs.

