7.3.3.3 EXPECTEDNESS

Anticipated Adverse Events (AAE) are considered to be those known, in terms of nature, severity and frequency, to be associated with the use of the test materials.

The following events have been identified as possible device-related adverse events of **sensor insertion and wear**:

- Excessive pain or discomfort from either system deployment or during wear period (8 or greater on a 10-point Likert scale)
- Excessive bleeding, defined as requires removal of the device to stop bleeding
- Hematoma, defined as induration at the sensor insertion location (ecchymosis is a known consequence of needle skin puncture or pressure from sensor pod and will not be captured as an AE)
- Edema from sensor and/or adhesive tape that is significant and non-resolving within 48 hours of sensor pod removal
- Erythema from sensor and/or adhesive tape that is significant and non-resolving within 48 hours of sensor pod removal
- Local infection, defined as presence of pus at either sensor wire or sensor pod site
- Sensor or introducer needle fracture during insertion/wear/removal

Information regarding device-related AEs that occur during the study will be entered into appropriate CRFs. Such information will include, at a minimum:

- Date of event
- Severity
- Outcome
- Resolution of event

PI will be responsible for determining whether an adverse event (AE) is expected or unexpected. An AE will be considered unexpected if the nature, severity, or frequency of the event is not consistent with the risk information previously described for the study intervention.

TIME PERIOD AND FREQUENCY FOR EVENT ASSESSMENT AND FOLLOW-UP

The occurrence of an adverse event (AE) or serious adverse event (SAE) may come to the attention of study personnel during study visits and interviews of a study participant presenting for medical care, or upon review by a study monitor.

All AEs including local and systemic reactions not meeting the criteria for SAEs will be captured on the appropriate case report form (CRF). Information to be collected includes event description, time of onset, clinician's assessment of severity, relationship to study product (assessed only by those with the training and authority to make a diagnosis), and time of resolution/stabilization of the event. All AEs occurring while on study must be documented appropriately regardless of relationship. All AEs will be followed to adequate resolution.

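### The only criterion given for the safety set, an example of at least 10 days of CGM use, would leave out people whose wear ends early because of a device harm

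*Combined protocol and SAP*

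**What the plan says.** Section 8.3 lists four analysis sets. The intention-to-treat set is fixed as everyone randomised. The safety set is the subset "for whom safety analyses will be conducted (e.g., participants who use the CGM for at least 10 days of study intervention". This is worded as an example, but it is the only criterion offered. Section 8.4 only points back to the hypotheses text, and 8.1 does not mention a safety set. The modified intention-to-treat set uses the same wear condition with an alternative attached: "participants who use the CGM for at least 10 days of study intervention and/or have acceptable amount of follow-up outcome data".

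Other sections link device harm to short wear. Section 6.1 states: "Sensors will be removed if prolonged bleeding or severe pain occurs". Section 7.3.3.3 lists among the anticipated device events "Excessive bleeding, defined as requires removal of the device to stop bleeding". Section 2.3.1 (1.d) says that "inserting the sensor could cause infection (<1%), bleeding or pain (~10" (the last figure is a percentage).

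The planned wear differs by part of the study. It is 10 days of blinded CGM in Aim 1 and in the Aim 2 run-in, then 4 weeks of real-time CGM and up to 4 weeks of blinded CGM in the two randomised phases (4.1, 5.6.1). One sensor lasts up to 10 days (5.7.2). For the 4-week phases, 5.6.1 says: "Participants will be trained to replace the G6 sensors at home during those 4 weeks".

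**The concern.** A safety population should not depend on how well the person tolerated the device. Under the 10-day example, someone whose sensor comes out early for bleeding or pain, and who does not resume wear, has the event of interest and is dropped because of it. Rates of insertion-site events computed on the remaining people could then be too low. If the and/or in the modified intention-to-treat definition is read as or, the same person could count for efficacy and not for safety.

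The scope of the 10 days is also open, so two analysts could build different sets:

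- **Which aim.** The intervention section includes Aim 1 ("Aim 1. Study Overview/Procedures for Aim 1a and Aim 1b: In this prospective observational cohort study"), yet 4.1 says of that aim: "No therapy adjustment or interventions will be made by the study team during this period".
- **Which wear.** Sections 4.1 and 5.6.1 use the word intervention for real-time CGM, while 4.4 and 6.1 use it for CGM in general. Whether blinded control-phase wear counts is therefore unclear.
- **How days are counted.** The text does not say whether they are cumulative, consecutive or per phase.

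What is at stake is the reported tolerability of the sensor. Section 2.2 says factory-calibrated sensors have not been studied in this population.

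**Working it through.** The plan states no figure for this set, so there is nothing to reproduce. The check has two parts.

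**1. Who could fall below 10 days under each reading**

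| Reading | Planned wear | Consequence |
|---|---|---|
| Aim 1 | 10 days (one full sensor life) | Any early removal without completed re-wear excludes the person |
| Run-in only (person leaves before randomisation) | 10 days | Same |
| One 4-week Aim 2 phase | 28 days; 28/10 = 2.8, about 3 sensors | Losing one full sensor period leaves 28 − 10 = 18 days, so mainly early dropouts are lost |
| Aim 2, run-in days counted cumulatively | At least 7 days to be randomised (5.9), then up to 28 + 28 = 56 | 10 − 7 = 3 more days suffice, so almost nobody is lost |
| Aim 2, real-time wear only | 28 days in one phase | Anyone who leaves during a control phase that comes first has no qualifying days |

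If a 10-day blinded wear has to meet the minimum by itself, people with 7 to 9 days of readings who met the adherence rule in 5.9 would also be left out. That is a reason to doubt that this reading was intended.

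**2. Effect on an event rate**

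Let p be the true share of people with an insertion-site event, f the share of affected people ending below 10 days, and d the share of unaffected people ending below 10 days. Then

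safety-set rate = p(1 − f) / [p(1 − f) + (1 − p)(1 − d)].

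Example: p = 0.10, f = 0.25, d = 0 gives 0.075 / (0.075 + 0.90) = 7.69%.

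| f | p = 10%, d = 0 | p = 5%, d = 0 | p = 10%, d = 10% | Affected people left out per 100 inserted, p = 10% (100pf) |
|---|---|---|---|---|
| 0 | 10.00% | 5.00% | 10.99% | 0 |
| 5% | 9.55% | 4.76% | 10.50% | 0.5 |
| 10% | 9.09% | 4.52% | 10.00% | 1 |
| 25% | 7.69% | 3.80% | 8.47% | 2.5 |
| 50% | 5.26% | 2.56% | 5.81% | 5 |
| 100% | 0% | 0% | 0% | 10 |

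The odds in the set equal the true odds times (1 − f)/(1 − d). The rate is understated only when f exceeds d, is unbiased when they are equal, and is overstated when d is larger.

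All values of p, f and d are assumptions. The 10% takes its size from 2.3.1, but that figure covers bleeding or pain of any severity, whereas removal is for prolonged bleeding or severe pain. High values of f are therefore hard to combine with p = 10%, and the last row is only a limiting case. For the 45 Aim 2 completers planned, p = 10% and f = 5%, 10% and 25% give 45 × 0.10 × f = 0.2, 0.45 and 1.1 affected people left out.

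**The case against.** The strongest reply is that little depends on this set. Section 8.1 specifies no analysis on it. The hospitalisation and emergency-visit outcome is a secondary outcome with its own method and is not tied to the safety set. All adverse events are documented from consent, whatever their relationship to the device (7.3.3.3). They are summarised without a wear condition (7.3.5) and reviewed by arm (9.1.6). Section 6.1 commits the clinical study report to covering all the safety data. This stands, and it limits the effect to rates computed on the safety set.

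Second, the list in 8.3 seems written for the randomised trial, where the effect is smallest. Sensors failing in the first 24 hours are replaced (5.9), and the run-in can be extended for adhesive or sensor failure (5.4). This stands in part. Those rules address failed sensors and do not expressly cover removal for bleeding or pain, and 5.7.4 caps insertion attempts after failure at two. Nothing in 8.3 restricts the safety set to Aim 2.

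Third, the criterion is only an example. That is true, but without it the set has no definition at all.

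A reader might go further and infer that early device harms will go unreported, or that the Aim 2 device-event rate will be materially understated. The documents support neither. Recording and reporting do not depend on wear time, and under cumulative counting or sensor replacement few randomised participants would fall short.

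**Conclusion.** The criterion as exemplified is unsuitable for a safety set and should be replaced. If applied, it selects on tolerating the device and could understate insertion-site event rates in any analysis run on that set. The size is unknown, because the documents do not give the share of affected people who end below 10 days. The effect is greatest in Aim 1 and among people who leave during the run-in, where 10 days is the whole planned wear. For randomised Aim 2 participants it is small or nil if days are cumulative or sensors are replaced. The downward direction assumes that affected people fall short more often than unaffected people. The consequence is for reported safety-set rates and not for participant protection.

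**What to change.** In 8.3, replace the example with a fixed definition: all participants with at least one sensor insertion attempted, blinded or real-time, with no minimum wear time. Report Aim 1 and Aim 2 separately. Aim 1 participants may go on to Aim 2 (5.1), so a single pooled set would mix an observational cohort with a cross-over trial and could count people twice. In Aim 2, assign each event to the run-in, real-time, wash-out or control phase in which it began. Keep any 10-day condition for efficacy sets only, and state there whether days are cumulative or per phase.

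The cost is a few sentences in 8.3. No new data collection is needed, because reportable events are already recorded from consent, and no clinical procedure changes.

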8.4 STATISTICAL ANALYSES

See above 9.1

8.4.1 PLANNED INTERIM ANALYSES

We plan to perform interim analysis on the primary endpoint every 6 months and/or when half of the subjects have been randomized. The trial will be stopped if there is evidence beyond a reasonable doubt of a difference in the rate of death (two-sided alpha level, <0.01) between the treatment groups.

8.4.2 SUB-GROUP ANALYSES

We will adjust the analysis of the primary endpoint based on age, sex, race/ethnicity or other demographic characteristic(s).

9 SUPPORTING DOCUMENTATION AND OPERATIONAL CONSIDERATIONS

9.1 REGULATORY, ETHICAL, AND STUDY OVERSIGHT CONSIDERATIONS

9.1.1 INFORMED CONSENT PROCESS

The Informed Consent Form must be approved by the IRB. The informed consent process fully apprises the subjects of the risks and benefits to them and to society for participating in the study. Each Subject must provide informed consent before participating in the study.

If the Subject understands and agrees to participate in the study, the Subject will sign and date the Informed Consent Form and the signature will be witnessed. Each Subject is given an unsigned copy of the Informed Consent Form. If a subject has questions about his/her rights, the subject may contact a member of the IRB.

9.1.1.1 CONSENT/ASSENT AND OTHER INFORMATIONAL DOCUMENTS PROVIDED TO PARTICIPANTS

Consent forms describing in detail the study intervention, study procedures, and risks are given to the participant and written documentation of informed consent is required prior to starting intervention/administering study intervention. The following consent materials are submitted with this protocol: Food record, Glucose diary, and SMBG log.

9.1.1.2 CONSENT PROCEDURES AND DOCUMENTATION

Informed consent will be initiated prior to the individual's agreeing to participate in the study and continues throughout the individual's study participation. Consent forms will be Institutional Review Board (IRB)-approved and the participant will be asked to read and review the document. The investigator and/or trained coordinator will explain the research study to the participant and answer any questions that may arise. A verbal explanation will be provided in terms suited to the participant's comprehension of the purposes, procedures, and potential risks of the study and of their rights as research participants. Participants will have the opportunity to

carefully review the written consent form and ask questions prior to signing. The participants will have the opportunity to discuss the study with their family or surrogates or think about it prior to agreeing to participate. The participant will sign the informed consent document prior to any procedures being done specifically for the study. Participants will be informed that participation is voluntary and that they may withdraw from the study at any time, without prejudice. A copy of the informed consent document will be given to the participants for their records. The informed consent process will be conducted and documented in the source document (including the date), and the form signed, before the participant undergoes any study-specific procedures. The rights and welfare of the participants will be protected by emphasizing to them that the quality of their medical care will not be adversely affected if they decline to participate in this study.

